3.2 Randomization

Not applicable, as all study subjects will be assigned to a single treatment, LL-BMT1 lenses.

3.3 Schedule of Evaluations and Analysis Visit Windows

The schedule of visits and procedures are provided in the study protocol, LL-BMT10001, version 1.2, section 1.3. The study consists of a screening period, 2 acclimation periods where the subject wears 2 sets of nonmedicated lens for 1 week each, 1 treatment week where the subject wears 1 set of LL-BMT1

lenses for 1 week, and a follow-up visit after lens removal. Visit days and windows are summarized in the table below:

Visit	Target Day of the Visit	Visit Windows (Days) for Analyses
Visit 1 - Screening	-45 to -14	< -14
Visit 2 – Acclimation	-14	-14
Visit 3 – Acclimation	-7	-7
Visit 4 – Acclimation	-6	-6
Visit 5 – Baseline	0	0
Visit 6 – LL-BMT1 Lens Insertion	1	1
Visit 7 – On-treatment	4	4
Visit 8 – End of treatment	7	7
Visit 9 – Follow-up	8	8
Visit 10 – Conditional Follow-up / End of study	9	9

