## 7.3 LOST TO FOLLOW-UP

A patient will be considered lost to follow-up per Principal Investigator discretion and upon consultation with the Sponsor upon failure to adhere to the protocol.

The following actions must be taken if a patient fails to return to the clinic for a required study visit:

- The site will attempt to contact the patient and reschedule the missed visit on the following day and counsel the patient on the importance of maintaining the assigned visit schedule and ascertain if the patient wishes to and/or should continue in the study.
- Before a patient is deemed lost to follow-up, the investigator or designee will make every effort to regain contact with the patient (where possible, 3 telephone calls and a certified letter to the patient's last known mailing address or local equivalent methods). These contact attempts should be documented in the patient's medical record or study file.

- Should the patient continue to be unreachable, he or she will be considered to have withdrawn from the study with a primary reason of lost to follow-up.

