Unscheduled visits can be included if safety concerns arise. Additional examinations may be performed as necessary to ensure the safety and wellbeing of patients during the study. eCRFs should be completed for each unscheduled visit.

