Study visits and assessments should be rescheduled at the discretion of the Investigator when there is a perceived increased risk of coronavirus transmission to patients and/or investigational site staff.

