6.8 Secondary Analysis

There will be both safety and efficacy assessments in the secondary analysis.

The secondary safety analysis will consist of identifying the following:

- Percent of patients with ≥ 5 mmHg increase from baseline in IOP at each visit
- “Abnormal” and “Severe” slit-lamp biomicroscopy findings at the Baseline, Day 1, and Day 7 Visits
- Contact lens protein deposits at the Day 7 Visit
- Change from Baseline in CLDEQ-8 results at the Day 7 Visit

The secondary efficacy analysis will consist of identifying the change from baseline in IOP at each visit. Study eyes only within the modified intent-to-treat population will be used for this part of the analysis.

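### SAP 3.3 gives each visit a one-day analysis window, but the protocol allows rescheduling, so a late visit falls in no window or in the next visit's window

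*SAP*

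**What the plan says.** The table in SAP 3.3 has one column for the target day and a separate one headed "Visit Windows (Days) for Analyses". For Visits 2 to 10 the second column repeats the target day and allows no days either side. The rows that matter most are "Visit 7 – On-treatment" (Day 4), "Visit 8 – End of treatment" (Day 7), "Visit 9 – Follow-up" (Day 8) and the conditional follow-up (Day 9). The SAP does not say what happens to a visit done on another day. It has no nominal-visit rule, and SAP 6.3 rules out imputation.

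The protocol expects that visits may move. For a patient who does not attend, Protocol 7.3 says: "The site will attempt to contact the patient and reschedule the missed visit on the following day". Protocol 10.2 adds, for times of raised coronavirus risk: "Study visits and assessments should be rescheduled at the discretion of the Investigator". It sets no limit in days. The schedule in Protocol 1.3 gives IOP a clock-time tolerance of one hour but gives visits no tolerance in days.

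The summaries that depend on visit assignment are in SAP 6.8: "The secondary efficacy analysis will consist of identifying the change from baseline in IOP at each visit", the percentage of patients with an IOP increase of at least 5 mmHg at each visit, and the slit-lamp, lens-deposit and CLDEQ-8 results tied to the Day 7 Visit.

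**The concern.** The end-of-treatment, follow-up and conditional follow-up visits fall on consecutive days (7, 8 and 9). With one-day windows, the shift of one day named in Protocol 7.3 is enough to move a reading from one of these visits to the next. A late Day 4 visit has no neighbouring window and falls out altogether.

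By-visit IOP change is the only efficacy endpoint, and there are five patients. One misplaced record therefore changes a visit's mean, median and range noticeably. The Visit 8 case is the worst, because the record lands among readings taken under different conditions.

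**Working it through.** **Inputs.** Analysis windows: SAP 3.3. Shift of one day: Protocol 7.3. Longer shifts: Protocol 10.2, which sets no limit. Treated patients: five (SAP 3.1). IOP clock times and procedures per visit: Protocol 1.3. The plan states no figure on this point to reproduce.

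**Step 1, on-time visits.** All nine of Visits 2 to 10 map to their own window when done on the target day. The table works if nothing moves.

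**Step 2, each visit after lens insertion shifted by one day.** Actual day = target day + 1, then look up the window.

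| Visit | Target day | Actual day | Window it falls in |
|---|---|---|---|
| 7 On-treatment | 4 | 5 | none |
| 8 End of treatment | 7 | 8 | Visit 9 |
| 9 Follow-up | 8 | 9 | Visit 10 |
| 10 Conditional follow-up | 9 | 10 | none |

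Over all of Visits 2 to 10, none of the nine shifted visits maps to itself. Five fall in no window (Visits 2, 4, 6, 7 and 10) and four fall under another visit (3, 5, 8 and 9). For Visits 2 to 6 this depends on how study day is anchored, which the SAP does not define. If Day 1 is the actual date of first LL-BMT1 insertion, a late baseline or insertion moves the anchor with it. Visits 7 to 10 are affected under either anchor, so the point rests on those.

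**Step 3, a shift of two days.** Visit 7 (Day 6), Visit 9 (Day 10) and Visit 10 (Day 11) fall in no window. Visit 8 (Day 9) falls under Visit 10.

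**Step 4, size per slip.** 1/5 = 20% of the patients at that visit. Visit 10 is held only for patients who meet the Day 8 IOP condition, so its denominator may be below five and the share larger.

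**Step 5, what is mixed when Visit 8 is late.** A Visit 8 IOP is read 3 minutes after lens removal, nominally at 4 pm. A Visit 9 IOP is scheduled for 8 am, with the lenses out since the previous day. Filed by day, the late Visit 8 reading joins the Visit 9 summary. Visit 9 schedules no biomicroscopy, contact lens assessment or CLDEQ-8, so those results would sit under a visit with no matching analysis and be absent from the Day 7 summaries.

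**Step 6, whether wider windows would solve it.** With windows from 0 to +1 day, Visit 8 covers Days 7–8, Visit 9 covers Days 8–9 and Visit 10 covers Days 9–10. Visits 8 and 9 then share Day 8, and Visits 9 and 10 share Day 9. With ±1 day, Visits 8 and 10 also share Day 8. Calendar windows cannot separate these visits once any slip is allowed.

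**The case against.** The strongest reply is that SAP 3.3 states no allocation algorithm. On this view the table restates the schedule with zero tolerance, an off-day visit is a deviation to be counted under SAP 6.2, and a programmer would use the visit label on the eCRF. That practice would give sensible results. However, the column stands apart from the target-day column and is labelled as being for analyses, and nowhere does the SAP say that nominal visits are used. A plan meant to pre-specify should not rely on the programmer setting its own table aside.

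The triggers are also limited. The wording in Protocol 7.3 could mean that contact, rather than the visit, takes place on the following day; Protocol 10.2 allows rescheduling without it. Rescheduling for respiratory symptoms requires lens removal during treatment, so that route does not produce a late Visit 8 with lenses still being worn.

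A reader might infer four stronger things that the documents do not support:

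- **On-lens IOP pooled with off-lens IOP.** All on-treatment IOP is read after lens removal (Protocol 1.3 and 8.2). The contrast is a reading just after removal against one with the lens out since the previous day, at different clock times.
- **Day 7 safety results lost.** They would be missing from the by-visit summary. Protocol 9.4.7 plans line listings for every patient, and no competing result is scheduled on Day 8, so they remain traceable.
- **The primary endpoint is affected.** It is not: SAP 6.7 defines treatment-emergent AEs by onset date.
- **A slip is likely.** The documents give no rate of late attendance, so any probability would reflect only the rate assumed.

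**Conclusion.** The point holds as a defect in a stated analysis rule that takes effect only if a visit slips. Applied as written, SAP 3.3 gives the wrong by-visit result for any of Visits 7 to 10 done one day late: two fall in no window and two fall under the next visit. Each slip affects one of five patients (20%) in that visit's secondary summaries, assuming all five reach the visit.

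The damage is descriptive. The SAP plans no hypothesis test. If the exploratory Wilcoxon test in Protocol 9.4.1 were run, its smallest two-sided p-value is 2/2^5 = 0.0625 with five patients and 2/2^4 = 0.125 with four, so no 5% conclusion is at stake. The reason to correct the rule is that in so small a study the by-visit IOP summaries are the whole efficacy result, and the correction is simple.

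**What to change.** Before database lock, amend SAP 3.3 as follows:

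- Replace the single-day windows with analysis by nominal visit as recorded on the eCRF.
- Report the actual study day and the time since final lens removal with the by-visit results, and define the day from which study day is counted.
- List and flag every visit done off its target day.
- Keep readings after early lens discontinuation, or after loss of one lens, at their nominal visit, flagged.

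Do not reassign visits by lens status. Under Protocol 6.5.1 and 7.1, patients who stop the intervention continue with scheduled visits. If lenses came off for good on Day 4, a lens-status rule would label that reading as Visit 8 and the Day 7 reading as Visit 9, repeating the misfiling.

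The cost is a short edit to one SAP section and one extra listing, plus a check that the eCRF captures the time of final lens removal. Visit conduct does not change. The small downside is that wear time then varies by about a day within a nominal visit, which the reported actual day makes visible.

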4 ANALYSIS POPULATIONS

4.1 Intent-to-Treat Population

The intent-to-treat (ITT) population includes all patients who have LL-BMT1 lenses successfully inserted. This population of patients will be used to summarize protocol deviations.

4.2 Safety Population

The safety population includes all patients who have LL-BMT1 lenses successfully inserted.

5 STUDY VARIABLES/PARAMETERS

5.1 Primary Endpoints

The primary safety endpoint is the adverse event (AE) rate, defined to be $100 \times [\text{number of AEs} / \text{number of eyes exposed to treatment}]$.

5.2 Secondary Endpoints

The secondary safety endpoints include the following:

- AEs
- Concomitant medications
- Heart rate and blood pressure
- BCVA
- IOP
- Biomicroscopy
- Conjunctival hyperemia
- Percent of patients with ≥ 5 mmHg increase from baseline in IOP at each visit
- Abnormal slit-lamp biomicroscopy findings at the Baseline, Day 1, and Day 7 Visits
- Contact lens protein deposits at the Day 7 Visit
- Change from Baseline in CLDEQ-8 results at the Day 7 Visit

The secondary efficacy endpoint will be the change from baseline in IOP at each visit.

6 STATISTICAL ANALYSIS METHODS

There are no formal study hypotheses to be tested in this study. Safety and efficacy endpoints will be summarized using frequency, mean, median, standard deviation, min and max for continuous variables, and frequency and percentage for categorical variables.

6.1 Subject Disposition

The number and percentage of subjects screened, enrolled, completed treatment, completed study, and within each population will be summarized.

Individual subject disposition data will be listed.

6.2 Protocol Deviations

The number and percentage of protocol deviations will be presented using the intent-to-treat population.

6.3 Missing Data and Imputation

No Imputation will be conducted for this study.

6.4 Demographics and Baseline Characteristics

Baseline and demographic assessments will be presented descriptively using the safety population. Mean, median, standard deviation, min and max will be used for continuous variables, while number and percentage will be used to describe categorical variables.

6.5 Prior and Concomitant Medications

Prior and concomitant medication will be coded using the World Health Organization Drug Dictionary (WHO DD), September 2020. The number and percentage of subjects who reported taking prior and/or concomitant medications will be summarized using the safety population.

Individual subject prior and concomitant medication data will be listed.

6.6 Medical History

The number and percentage of past and concurrent medical conditions will be summarized using the safety population.

Individual subject medical history data will be listed.

6.7 Primary Analysis

The primary safety analysis will be treatment-emergent adverse events, defined to be any AE with an onset date equal to or after the date of the first insertion of the study lens and during the treatment, using the safety population.

Pre-existing AEs, those identified after enrollment but before treatment with LL-BMT1, will be tabulated for all consented patients. The rate of adverse events will be defined as $100 \times [\text{number of AEs} / \text{number of eyes exposed to treatment}]$.

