## 8.3 ADVERSE EVENTS AND SERIOUS ADVERSE EVENTS

### 8.3.1 DEFINITION OF ADVERSE EVENTS

An AE is any untoward medical occurrence in a patient or clinical investigation patient administered a pharmaceutical product and that does not necessarily have a causal relationship with this treatment. An AE can therefore be any unfavorable and unintended sign (including an abnormal laboratory finding), symptom, or disease temporally associated with the use of a medicinal (investigational) product, whether or not related to that product. Worsening of the pterygium is not an AE, unless the lesion growth is greater than expected.

Treatment-emergent AEs are any AEs with an onset date equal to or after the date of the first insertion of the study lens and during the treatment. A pre-existing event that worsens after the first treatment date is considered a treatment-emergent event.

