#### 8.3.4 TIME PERIOD AND FREQUENCY FOR EVENT ASSESSMENT AND FOLLOW-UP

Any medical condition that is present at the time that the patient is screened will be considered as medical history and not reported as an AE. However, if the study patient’s condition deteriorates at any time after enrollment, it will be recorded as an AE.

Changes in the severity of an AE will be documented to allow an assessment of the duration of the event at each level of severity to be performed. AEs characterized as intermittent require documentation of onset and duration of each episode.

The investigator or qualified designee will record all reportable events with start dates occurring any time after informed consent is obtained until 7 days (for non-serious AEs) or 30 days (for SAEs) after the last day of study participation. Patient will be told to call and notify the investigator of such events that occur during this period after the end of study visit. Events will be followed for outcome information until resolution or stabilization.

AEs will be monitored throughout the study beginning at the time the patient signs the informed consent for this study. At each post-Baseline visit, the investigator will begin by querying for AEs by asking each patient a general, non-directed question, such as “How have you been feeling since the last visit?” Directed questioning and examination will then be done as appropriate. All reported AEs will be documented on the appropriate eCRF, including seriousness, severity, relationship to study drug, action taken, and outcome (including date of resolution or stabilization, if AE is not ongoing). If AEs occur, the first concern will be the safety of the study patients.

If a patient becomes pregnant during the study, the investigator must inform the Sponsor and collect follow-up data regarding the pregnancy, birth, and status of the child. The Sponsor will provide special CRFs for data collection in the case of pregnancy. Follow-up should be continued until study close-out at the study center. After close-out, the Sponsor's Safety designee will continue to obtain follow-up information. Pregnancy should be recorded as a protocol deviation. Pregnancy is not an AE; however, any complication related to pregnancy would be considered an AE.

---

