### 9.4.2 SAFETY ANALYSES

Analysis of treatment-emergent AEs will be conducted based on the safety population. Safety endpoints include:

- AEs
- Concomitant medications
- Heart rate and blood pressure
- BCVA
- IOP
- Biomicroscopy
- Conjunctival hyperemia

Ocular events will be reported on an eye level, while non-ocular events will be on a patient level.

AEs will be coded using the Medical Dictionary for Regulatory Activities (MedDRA). For each AE reported, the number and percent of patients/eyes will be tabulated based on the preferred term and ocular and non-ocular AEs will be reported separately. The tables will be generated by relationship to treatment as well as by system organ class and severity.

The primary safety endpoint is the AE rate ( $100 \times [\text{number of AEs} / \text{number of eyes exposed to treatment}]$ ). The modified safety set will be used for a sensitivity analysis of the primary safety endpoint.

*Secondary safety endpoints:*

- Percent of patients with  $\geq 5$ -mmHg increase from baseline in IOP at each visit
- Abnormal slit-lamp biomicroscopy findings at the Baseline, Day 1, and Day 7 Visits
- Contact lens protein deposits at the Day 7 Visit
- Change from baseline in CLDEQ-8 results at the Day 7 Visit

Pre-existing AEs, those identified after enrollment but before treatment with LL-BMT1, will be tabulated for all consented patients.

---

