1.1 Changes from Protocol

Not applicable.

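### SAP 6.7 defines treatment-emergent AEs by onset date alone and, without declaring it, omits the protocol's rule that a pre-existing event which worsens on treatment also counts

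*SAP*

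**What the plan says.** Protocol 8.3.1 defines treatment-emergent AEs in two limbs. The first is new onset: "Treatment-emergent AEs are any AEs with an onset date equal to or after the date of the first insertion of the study lens", and during treatment. The second is worsening: "A pre-existing event that worsens after the first treatment date is considered a treatment-emergent event".

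Protocol 9.4.2 builds the AE analysis on this concept without redefining it: "Analysis of treatment-emergent AEs will be conducted based on the safety population".

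SAP 6.7 names treatment-emergent AEs as the primary safety analysis and defines them as "any AE with an onset date equal to or after the date of the first insertion of the study lens and during the treatment". This is the first limb only. The same section then says: "Pre-existing AEs, those identified after enrollment but before treatment with LL-BMT1, will be tabulated for all consented patients". It does not mention worsening, and no other SAP section does. Under changes from protocol, SAP 1.1 reads "Not applicable".

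On the endpoint, SAP 5.1 says "The primary safety endpoint is the adverse event (AE) rate" and defines it as 100 times the number of AEs divided by the number of exposed eyes. SAP 6.7 repeats that formula, and Protocol 9.4.2 gives the same one. None of the three says that the numerator is restricted to treatment-emergent AEs.

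**The concern.** The two documents give different definitions for the primary safety analysis, and the difference is not declared. A programmer working from the SAP would code the onset test alone.

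The design makes the second limb relevant. AEs are collected from informed consent. Before Day 1 a patient may go through washout of earlier IOP treatment and wears nonmedicated lenses for two weeks, with slit-lamp and visual acuity examinations at each visit. There is thus an observed pre-treatment period in which an AE can start. Aggravation of such an AE once the drug-printed lens is in place is information about the product's safety, and the protocol chose to count it. Under the SAP it would be classed with events that preceded treatment.

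**Working it through.** **Figures in the plan.** The plan gives no expected AE rate to reproduce. Its only reproducible sample-size figure is the number consented: 5 / (1 − 0.10) = 5.56, rounded up to 6, and 5 / (1 − 0.20) = 6.25, rounded up to 7. This agrees with the stated maximum of 7. The present point does not depend on it.

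**Step 1: the two definitions.**

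| Event | Protocol 8.3.1 | SAP 6.7 |
|---|---|---|
| Starts on or after first insertion, during treatment | Treatment-emergent | Treatment-emergent |
| Starts before insertion, does not worsen | Not treatment-emergent | Not treatment-emergent |
| Starts before insertion, worsens after the first treatment date | Treatment-emergent | Not treatment-emergent |

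The documents differ only in the third row.

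**Step 2: does a worsened event keep its earlier onset date?** Protocol 8.3.4 says "Changes in the severity of an AE will be documented to allow an assessment of the duration of the event at each level of severity". Measuring duration at each severity level implies one AE record with one onset date and several severity periods. On that reading a worsened AE fails the SAP's onset test. The documents do not state the eCRF dating convention, so this is an inference.

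**Step 3: which events are affected?**
- A condition present at screening is medical history. If it deteriorates after enrollment, Protocol 8.3.4 has it recorded as an AE. If that AE is dated at the deterioration, SAP 6.7 already captures it.
- AEs related to the nonmedicated lens are largely removed by inclusion criterion 7 and Protocol 4.1.
- What remains is mainly AEs not related to the nonmedicated lens that start between consent and Day 1 and worsen on LL-BMT1.

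**Step 4: size.** Inputs are 5 patients with both eyes treated (Protocol 4.1), so 10 exposed eyes, and the SAP 5.1 formula. Assume the numerator means treatment-emergent AEs.
- One omitted worsening: 100 × 1/10 = 10 per 100 eyes.
- A bilateral worsening counted per eye: 100 × 2/10 = 20 per 100 eyes.
- With 9 exposed eyes: 11.1 and 22.2. With 8: 12.5 and 25.0.

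Illustration with assumed counts:

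| New-onset AEs | Worsened pre-existing AEs | Rate, SAP 6.7 | Rate, Protocol 8.3.1 |
|---|---|---|---|
| 0 | 1 | 0 | 10 |
| 2 | 1 | 20 | 30 |
| 2 | 2 | 20 | 40 |

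The documents give no expected frequency for such events, so these figures show the effect per event and are not a forecast.

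**The case against.** There are five arguments on the other side.

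1. **The numerator is not explicitly treatment-emergent.** The formula counts AEs. Read literally, a worsened pre-insertion AE would be in the numerator anyway, along with pre-insertion AEs that never worsened. This stands as a condition on the size. The gap in the definition remains, since SAP 6.7 still makes treatment-emergent AEs the primary analysis.

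2. **Eligibility narrows the set.** A reader might picture mild hyperemia appearing during nonmedicated lens wear and becoming severe on LL-BMT1. That is not a sound leading example: inclusion criterion 7 and Protocol 4.1 bar patients with reactions to the nonmedicated lens. Footnote p of the Schedule of Activities leaves eligibility after AE questioning to the investigator. Those passages need reconciling with one another, but that is a separate matter and footnote p alone does not widen the set. AEs unrelated to the lens are not barred.

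3. **Deteriorating medical history may already be counted.** This stands if the AE is dated at deterioration. It does not cover AEs that began after consent.

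4. **Worsening would still be visible.** A reader might infer that such events disappear from the report. They do not have to: Protocol 9.4.7 plans line listings for each patient, and SAP 5.2 lists biomicroscopy, conjunctival hyperemia, BCVA, IOP and CLDEQ-8 change as safety endpoints. This stands, with one limit. The slit-lamp analysis in SAP 6.8 covers Baseline, Day 1 and Day 7, and the Day 1 examination precedes insertion, so Day 7 is its only on-treatment look.

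5. **The study is descriptive.** It has five patients, one arm, no formal hypothesis and no threshold on the rate. This stands and lowers the severity.

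**Conclusion.** The mismatch is real. SAP 6.7 omits the worsening limb of Protocol 8.3.1, nothing else in the SAP restores it, and SAP 1.1 does not declare the change. Followed as written, the SAP leaves out of its primary analysis an AE that began between consent and first insertion and worsened on LL-BMT1, and tabulates it as pre-existing.

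This rests on two assumptions: that the AE keeps its pre-insertion onset date, which Protocol 8.3.4 implies but does not state, and, for the effect on the rate, that the numerator means treatment-emergent AEs. If both hold, the effect is that shown in step 4 of the working. The documents do not support the stronger conclusion that the primary rate will certainly be understated.

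Severity: should-fix. The point concerns the primary safety analysis and is cheap to settle, but no test or decision rule depends on the result.

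**What to change.** - **SAP 6.7:** add the worsening limb of Protocol 8.3.1. An AE with onset before first LL-BMT1 insertion whose severity increases after the first treatment date counts as treatment-emergent, dated at the severity change and, for ocular events, assigned per eye. Derive it from the severity-change records that Protocol 8.3.4 already requires. Say also how a severity change on Day 1 itself is handled, since the onset limb includes that date and the worsening limb starts after it.
- **SAP 5.1 and 6.7:** state that the numerator of the AE rate is treatment-emergent AEs so defined. Without this, the first change does not settle the primary rate.
- **Alternative:** if the narrower definition is intended, declare and justify it in SAP 1.1.

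The cost is one sentence in 6.7, a clause in 5.1 and 6.7, and one derivation, with no new data. The only downside is that the reported rate may be less favourable. The change should be made before database lock.

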#### **Day 9 (Visit 10): Conditional follow-up assessment (If a patient's IOP is decreased from baseline by $\geq 3$ mmHg at the Day 8 Visit) / End of study**

- Concomitant medications
- AEs

- Heart rate and blood pressure
- IOP (measured at 8 am  $\pm$ 1 hour)

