### 4 STUDY DESIGN

#### 4.1 OVERALL DESIGN

This will be an open-label, phase 2a clinical study. Five patients with treated or treatment-naïve POAG or OHT in both eyes will be enrolled. All previously treated eyes will have a washout period prior to enrollment. At least one eye (called the study eye) will have untreated (after washout, if applicable) IOP between 22 mmHg and 34 mmHg (inclusive). If both eyes meet this criterion, then the eye with the higher IOP will be selected as the study eye. If the IOP in both qualified eyes is the same, then the right eye will be selected as the study eye. If the fellow eye does not meet this IOP criterion, it must have an untreated IOP (following washout, if applicable) within 5 mmHg of the study eye without exceeding the 34-mmHg maximum. For all enrolled patients, both eyes will be treated, and all tests will be performed separately on both eyes, but only the study eye will be included for efficacy analysis.

Beginning 2 weeks prior to the Baseline Visit, all patients will have a 2-week run-in acclimation period with a nonmedicated contact lens in each eye to ensure contact lens tolerability. The patient will be questioned about AEs related to the contact lens wear. The patient must have experienced no contact lens-related AEs in order to be eligible for the study. If a patient does not successfully complete the 2-week acclimation screening, that patient will be replaced until at least 5 patients successfully complete the acclimation screening. Those patients who have completed acclimation screening will be enrolled as patients for dosing with LL-BMT1. After insertion of the LL-BMT1 (medicated) lens, patients will be followed for 7 or 8 days for assessments of safety and IOP reduction.

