#### 4.2 SCIENTIFIC RATIONALE FOR STUDY DESIGN

This study is designed to examine the use of bimatoprost delivered via extended-wear contact lenses and assess the safety and efficacy of this drug device in a sample of patients. Both bimatoprost and the contact lens (as a nonmedicated lens) are FDA-approved, long-standing commercial products with well-characterized safety and effectiveness profiles. All patients will attend a follow-up visit on Day 8, and if IOP at that visit is decreased from baseline by  $\geq 3$  mmHg, patients will attend a conditional follow-up visit on Day 9 in order to reassess IOP.

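### The primary AE analysis in effect ends at lens removal, the AE-rate formula states no window, and the SAP narrows the safety population without declaring it

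*SAP*

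**What the plan says.** **Window.** SAP 6.7 limits the primary safety analysis to AEs with "onset date equal to or after the date of the first insertion of the study lens and during the treatment, using the safety population". Protocol 8.3.1 closes the window in the same way and adds that a pre-existing event which worsens after first treatment counts as treatment-emergent. SAP 6.7 does not carry that sentence over. Its only other AE table covers events found before LL-BMT1 treatment.

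**Endpoint.** SAP 5.1 states: "The primary safety endpoint is the adverse event (AE) rate, defined to be" 100 times the number of AEs over the number of eyes exposed. Protocol 9.4.2 gives the same formula ("The primary safety endpoint is the AE rate"). Neither says which AEs count, nor does the repeat of the formula in SAP 6.7.

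**End of treatment and follow-up.** Protocol 6.1.2 treats the Day 7 Visit, when the lenses are taken out, as the end of treatment. SAP 3.3 lists the treatment week and the visit after lens removal as separate parts of the study. Protocol 4.1 says that after insertion "patients will be followed for 7 or 8 days for assessments of safety and IOP reduction", and Protocol 4.2 that "All patients will attend a follow-up visit on Day 8". The schema then has "Day 9 (Visit 10): Conditional follow-up assessment", which depends on the IOP response. AEs are asked about at both visits.

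**Population.** Protocol 9.3 defines the safety population by eye contact with an LL-BMT1 lens. SAP 4.2 requires successful insertion, which is also the ITT criterion in SAP 4.1. SAP 1.1 reports no changes from the protocol.

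**The concern.** Safety is the primary objective. The protocol brings every patient back the day after lens removal and asks about AEs, yet the primary analysis as worded in SAP 6.7 does not reach that day. An analyst who follows SAP 6.7 and one who follows the formula in SAP 5.1 could report different primary results from the same data.

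The population change acts at the other end of exposure. A patient whose eye touched the lens but in whom insertion failed belongs to the protocol's safety population and not to the SAP's.

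What is at stake is an incomplete or ambiguous primary safety figure. There is no hypothesis test and no decision threshold for it to distort.

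**Working it through.** The plan gives no figure for this point. Its only derived number is the count consented: 5/(1 − 0.10) = 5.56, rounded up to 6, and 5/(1 − 0.20) = 6.25, rounded up to 7. This agrees with the stated maximum of 7 and does not bear on what follows.

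**1. Dates.** First insertion is Day 1 and end of treatment is Day 7 (Protocol 6.1.2). Follow-up under Protocol 4.1 runs to Day 1 + 7 = Day 8 or Day 1 + 8 = Day 9. Recording under Protocol 8.3.4 continues for 7 days after last participation for non-serious AEs (8 + 7 = Day 15, or 9 + 7 = Day 16) and for 30 days for SAEs (8 + 30 = Day 38, or 9 + 30 = Day 39).

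| Follow-up counted | Last day | Days after Day 7 |
|---|---|---|
| Scheduled visits | 8 or 9 | 1 of 8, or 2 of 9 |
| Non-serious AE recording | 15 or 16 | 8 of 15, or 9 of 16 |
| SAE recording | 38 or 39 | 31 of 38, or 32 of 39 |

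**2. Early removal.** Protocol 7.1 asks patients taken off the lens to keep attending visits. If the lens is assumed to come off on Day 4, onset is counted on 4 dates (Days 1 to 4) instead of 7, while the patient still adds 2 eyes to the denominator.

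**3. Where an AE is counted.**

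| Onset | SAP 6.7 primary analysis | SAP 6.7 pre-treatment table | Formula in SAP 5.1 |
|---|---|---|---|
| Before first insertion | No | Yes | Not stated |
| Insertion to lens removal | Yes | No | Yes |
| After lens removal | No | No | Not stated |

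**4. Weight of one event.** Eyes exposed = 5 × 2 = 10, so an event counted once adds 100/10 = 10 per 100 eyes. Protocol 9.4.2 says "Ocular events will be reported on an eye level, while non-ocular events will be on a patient level". If a bilateral ocular event is counted per eye, it adds 2 × 10 = 20. As an illustration, assume 2 AEs through Day 7 and 1 on Day 8. The rate is 100 × 2/10 = 20 under SAP 6.7 and 100 × 3/10 = 30 through Day 8, or 100 × 4/10 = 40 if the Day 8 event is bilateral and counted per eye.

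**5. Worsening.** Protocol 8.3.4 records a screening condition that deteriorates as an AE and documents changes in severity. The sentence missing from SAP 6.7 therefore matters mainly for AEs that begin between consent and first insertion and then worsen.

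**6. Population.** Assume one patient has both eyes touched by a lens, both insertions fail, and the other four patients have 2 AEs in total.

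| AEs in the failed-insertion patient | Contact definition | Successful-insertion definition |
|---|---|---|
| 1 | 100 × 3/10 = 30 | 100 × 2/8 = 25 |
| 0 | 100 × 2/10 = 20 | 100 × 2/8 = 25 |

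The rate can move in either direction.

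**The case against.** The strongest reply is that the endpoint itself has no cut-off. The formula counts AEs without qualification, and Day 7 is inferred from Protocol 6.1.2 because no last counted day is written. SAP 5.2 also lists AEs without qualification as a secondary safety endpoint, and SAP 6 says that safety endpoints will be summarised. Protocol 9.4.2 adds: "For each AE reported, the number and percent of patients/eyes will be tabulated based on the preferred term". Line listings are planned (Protocol 9.4.7). A reader might infer that a Day 8 AE disappears from all output. The documents do not support that, although Protocol 9.4.2 opens with treatment-emergent AEs, so its table may share the cut-off.

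The gap at Day 8 is also short. IOP is measured at 8 am ± 1 hour, so an AE dated Day 8 and known at the visit began in the 7 to 9 hours after midnight. An onset dated Day 7 is arguably already counted. Biomicroscopy is not scheduled that day. BCVA, IOP, heart rate and blood pressure are, however, and Protocol 8.2 turns clinically significant abnormal findings into AEs.

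Three further inferences go too far:
- That the SAP departs from the protocol on the cut-off. It inherits it from Protocol 8.3.1.
- That an omitted AE is likely. The documents give no frequency from which to say so.
- That the narrower population lowers the rate. Step 6 of the working shows both directions. A failed insertion is also probably rare, since the investigator inserts every lens and each patient has already had two nonmedicated insertions.

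These arguments limit the certainty and size of the point. They do not supply a single stated numerator: if the formula governs, it has neither start nor end; if SAP 6.7 governs, onset after removal is left out.

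**Conclusion.** The point holds, at moderate weight. SAP 6.7 and Protocol 8.3.1, read with Protocol 6.1.2 and SAP 3.3, end the primary AE window at lens removal. AEs that begin later are then in neither the primary analysis nor the pre-treatment table, and the rate formula does not settle the matter. The omitted sentence on worsening has a narrow effect. The change of safety population is a plain, undeclared difference from the protocol that matters only if an insertion fails.

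The size is 10 per 100 eyes for each event counted once, assuming all 5 patients are treated in both eyes. How often this would occur cannot be judged from the documents. The study is descriptive and no decision rests on the rate, so the harm is an incomplete or ambiguous primary safety figure.

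**What to change.** Amend the SAP before database lock.

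- **SAP 5.1 and 6.7.** State one numerator: AEs with onset or worsening from first contact with an LL-BMT1 lens through the Day 8 Visit, the last visit scheduled for everyone. Show it in two rows, through the date of final lens removal and after it. Apart from worsening events and failed insertions, the first row is the present during-treatment count.
- **Rescue medication.** Flag AEs with onset after its start. Protocol 6.5.1 already has the date and time recorded.
- **Later reports.** Tabulate AEs reported after the Day 8 Visit separately, because they reach the site through a conditional visit or the patient's own call. State which table takes an AE that began before that visit and was reported after it.
- **SAP 4.2.** Restore the Protocol 9.3 contact definition, and use the same eyes in numerator and denominator.
- **SAP 1.1.** Declare any difference from Protocol 8.3.1.

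The cost is SAP wording and a few AE table rows. The split uses dates only, but the removal date must be recorded where a patient takes out a lens at home (Protocol 10.2). The reported rate may rise and may include some events unrelated to the lens. Aligning the protocol text as well would need IRB approval (Protocol, Statement of Compliance).
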